6.5.4 Survival and Time to Clinical Events

Survival and time to hospitalizations and clinical events will be analyzed in the FAS, ERO, EPP, STF, and SRO analysis sets. Survival analyses that include follow-up beyond the placebo-controlled period will be analyzed in the ERO analysis set. The summaries and analyses of time to death or death equivalent are the same as specified in the M-SAP with the addition of baseline age as an additional covariate in adjusted models, with the addition that the endpoints of time to death independent of occurrence of death equivalents and time to each of the hospitalization and clinical events will be separately analyzed using the same models, and with an additional adjusted analysis that includes baseline serum NfL level as a covariate. Analysis of time to

King's stage 4a or 4b will accommodate interval censoring between ALSFRS-R assessments and will be stratified by baseline King's stage.

Listings of all participants in the FAS, ERO, EPP, STF, and SRO analysis sets will document whether each participant had died, had reached a death equivalent endpoint, or was alive and free of a death equivalent and the study day of death, death equivalent, or last known alive and free of a death equivalent for each analysis timepoint.

6.5.5 CAFS

The primary CAFS analysis is as specified in the MPRDR. Additional, unadjusted CAFS analyses are the same as specified in the M-SAP, including specification that pair-wise comparison of change in ALSFRS-R total score for participants who cannot be ranked by time to death or death equivalent is to the maximum follow-up time at which both participants have an observation, and with the following additions:

1. HHD upper and lower extremity percentage and SVC will be analyzed by CAFS by substituting change from baseline for those secondary efficacy endpoints in place of ALSFRS-R total score,
2. An additional set of CAFS analyses will use multiple imputation to extend follow-up of ALSFRS-R total score, HHD upper and lower extremity percentage and SVC for participants who early terminate, withdraw consent, or are lost to follow-up,
3. An additional set of CAFS analyses will use time to death alone independent of any death equivalent,
4. An additional set of CAFS analyses for ALSFRS-R total score, HHD upper and lower extremity percentage, and SVC will adjust rank scores in a linear model with the following covariates: time from ALS symptom onset, delta-FRS, baseline use of riluzole, and baseline use of edaravone, and
5. An additional set of CAFS analyses for ALSFRS-R total score, HHD upper and lower extremity percentage, and SVC will adjust rank scores in a linear model with the following covariates: time from ALS symptom onset, delta-FRS, baseline use of riluzole, baseline use of edaravone, and baseline serum NfL level..

The multiple imputation model used to extend follow-up of functional scores for participants who early terminate, withdraw consent, or are lost to follow-up will use linear regression with covariates of time since symptom onset, delta-FRS, baseline riluzole use, baseline edaravone use, and each observed functional score prior to a missing assessment.

Inference from CAFS analyses is supportive of inference from the Bayesian shared-parameter, repeated-measures model for the primary outcome and supportive of inference from the repeated-measures model for the secondary outcomes of HHD upper extremity score, SVC, and HHD lower extremity score. Primary inference from CAFS analyses will compare survival by time to death or death equivalent, will compare change in function to the last jointly observed time point, and will adjust for the specified covariates.

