3.0 (continued)	22 Jul 2022 (continued)	
Revision of Section 5.9 Survival to specify that time at risk begins at each participant's Baseline Visit and to specify that the date of PAV initiation, where applicable, will be imputed as the fifteenth day of a month if not specified more precisely.
 
Revision of Section 6.1 Analysis Sets to add the Efficacy Common Mode of Administration (ECM) analysis set, to remove the restriction on protocol deviations that could be considered for exclusion from the Efficacy Per-protocol (EPP) analysis set must be classified as major protocol deviations, to specify the time point at which data is excluded from the EPP analysis set in the case of time-dependent exclusions, and to specify that data from placebo participants from other regimens would not be excluded from the EPP analysis set due to non-adherence to protocol-specified dosing.
 
Revision of Section 6.2 Baseline Characterization to include ALSAQ-40 domain scores and SI.
 
Revision of Section 6.5.2 Repeated-measures Model to add a fixed term for treatment group (removing the shared-baseline assumption at the recommendation of the FDA) and to specify a separate supportive analysis that includes fixed terms for centered baseline serum NfL level, and centered baseline serum NfL level \times visit interaction.
 
Revision of Section 6.5.3 Random-slopes Model to add a fixed term for treatment group (removing the shared-baseline assumption) and to specify a separate supportive analysis that includes fixed terms for centered baseline serum NfL level, and centered baseline serum NfL level \times study month interaction.
 
Revision of Section 6.5.4 Survival and Time to Clinical Events to clarify that survival analyses that include follow-up beyond the placebo-controlled period will be analyzed in the ERO analysis set, to include baseline age as an additional covariate in adjusted models given strong prognostic value, and to specify an additional adjusted analysis that includes baseline serum NfL level as a covariate.
 
Revision of Section 6.5.5 CAFS to clarify that the primary CAFS analysis is specified in the ALS Master Protocol Recommended Statistical Analysis, Design and Simulation Report and to add two additional sets of CAFS analyses that adjust rank scores in linear models, one set that adjusts for time from ALS symptom onset, delta-FRS, baseline use of riluzole, and one set that adjusts

Version	Date	Description of Changes

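### The adjusted CAFS analyses omit baseline age, although CAFS ranks first on death and the SAP adds age to the adjusted models for that same outcome

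*SAP*

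**What the plan says.** SAP 6.5.5 describes two covariate-adjusted sets of CAFS analyses for ALSFRS-R, HHD upper and lower extremity percentage, and SVC. Item 4 adjusts the rank scores "in a linear model with the following covariates: time from ALS symptom onset, delta-FRS, baseline use of riluzole, and baseline use of edaravone". Item 5 has the same list extended by one marker, ending "baseline use of riluzole, baseline use of edaravone, and baseline serum NfL level". Age is in neither.

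The section closes by saying that "Primary inference from CAFS analyses will compare survival by time to death or death equivalent", using change in function to the last jointly observed time point, "and will adjust for the specified covariates". Function is compared only for pairs that survival cannot rank. The same section opens with "The primary CAFS analysis is as specified in the MPRDR".

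For time to death or death equivalent itself, SAP 6.5.4 takes over the M-SAP analyses "with the addition of baseline age as an additional covariate in adjusted models". The version 3.0 entry in the SAP's revision history gives the reason: the survival section was revised "to include baseline age as an additional covariate in adjusted models given strong prognostic value". According to that history, the adjusted CAFS sets entered the SAP in the same version.

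**The concern.** CAFS puts survival ahead of function. Its adjusted covariate list is the one used for the functional models (SAP 6.5.2 and 6.5.3), with no term for the predictor that the SAP singles out for survival. Version 3.0 carried baseline serum NfL into the mixed models, survival, CAFS, HHD0 and the placebo imputation, but carried age only into the survival and time-to-event models.

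CAFS has a real job here. It supports the primary result, and it supports HHD and SVC, whose lead model treats data missing because of death as missing at random (SAP 6.5.2). Age is recorded before treatment and cannot be affected by it. Neither regimen assignment nor treatment allocation is stratified by age; both are stratified by riluzole and edaravone use only (SAP 2.5 and 2.6). At stake are a possible small loss of precision and exposure to chance age imbalance in the analysis that ranks deaths.

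**Working it through.** **No figure to reproduce.** The protocol and SAP give no power, effect size, event rate or variance for CAFS. The size of the effect therefore has to be explored over assumptions.

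**Inputs from the documents.** 120 active and 40 placebo in the regimen (protocol summary); shared placebo from regimens B, C and D, number not stated (SAP 6.1); 24 weeks of placebo-controlled follow-up; item 4 covariates (SAP 6.5.5).

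**Assumed inputs.** 40 shared placebo participants per regimen, so 160 placebo in all (120 v 40 also run); 24-week risk of death or death equivalent 5% to 15%; death hazard ratio 1.3 to 1.6 per SD of age (taken as 10 years); correlation of age with functional change 0, 0.1 or 0.2; delta-FRS hazard ratio 1.8 per SD and correlation 0.4 with functional change.

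**Step 1: how much of CAFS is decided by death.** The share of pairs with at least one event is 1 − (1 − p)².
- p = 5%: 1 − 0.95² = 9.8%
- p = 10%: 1 − 0.90² = 19.0%
- p = 15%: 1 − 0.85² = 27.8%

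So most pairs are ranked on function, and a predictor of survival alone has limited leverage.

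**Step 2: the linear-model identity.** Ignoring the lost degree of freedom, SE with age / SE without age = √(1 − R²), where R² is the partial R² of age. Starting from 80% power at two-sided 0.05, new power = Φ[(1.960 + 0.842)/√(1 − R²) − 1.960].

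| Partial R² of age | SE reduction | Power |
|---|---|---|
| 0.01 | 0.5% | 80.4% |
| 0.02 | 1.0% | 80.8% |
| 0.06 | 3.0% | 82.4% |

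**Step 3: simulation of the item 4 model.** Deaths were ranked by time and survivors by function. Ranks were regressed on treatment and the item 4 covariates, with and without age (400 runs per setting; 120 v 160 and 120 v 40). Dropout and last-joint-visit comparisons were not modelled, and item 5 was not simulated.

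| Correlation of age with functional change | Change in SE when age is added |
|---|---|
| 0 (survival only) | 0.3% increase to 0.4% reduction |
| 0.1 | 0.5% to 1.4% reduction |
| 0.2 | 1.9% to 3.1% reduction |

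With a treatment effect, 120 v 160, hazard ratio 1.5 and about 7% deaths (2,000 runs), power without and with age was 69.6% and 70.1% at correlation 0, 69.6% and 70.9% at 0.1, and 72.2% and 73.9% at 0.2.

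**Step 4: chance imbalance.** The 95% range for the difference in mean age, in SD units, is ±1.96 × √(1/n₁ + 1/n₂).
- 120 v 160: 1.96 × √(0.00833 + 0.00625) = ±0.24 SD
- 120 v 40: 1.96 × √(0.00833 + 0.02500) = ±0.36 SD

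An imbalance at the edge of that range moves the unadjusted estimate by about 1.96 × √R² of its own standard errors: 0.20 at R² = 0.01, 0.28 at 0.02 and 0.48 at 0.06. Including age removes that shift in the trial at hand.

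**The case against.** The covariate list is coherent as it stands. Item 4 uses the same four covariates as the repeated-measures and random-slopes models and the CAFS imputation model, and CAFS is declared supportive of the repeated-measures model for HHD and SVC. A shared list makes the two easier to compare. This point has weight, but those models do not rank deaths and CAFS does, so matching them serves only its second component.

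The SAP calls age prognostic for survival and time-to-event outcomes only, and the working shows that this route alone yields almost nothing. That stands, and it limits the claim.

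CAFS is also low in the plan: "Inference from CAFS analyses is supportive of inference from the Bayesian shared-parameter, repeated-measures model for the primary outcome", and it is not in the testing sequence of SAP 6.5.1. Age is already covered by the adjusted survival models and by an age subgroup analysis (SAP 6.5.10). This bears on importance, not on whether the inconsistency exists.

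A reader might also infer that sharing placebo across regimens makes a systematic age difference likely. The documents do not support that. Regimens are assigned at random to participants eligible under the Master Protocol, only concurrently enrolling regimens contribute (SAP 2.5 and 6.1), and the protocol expects no systematic difference in the primary endpoint between controls (9.3). Ordinary chance imbalance is what remains.

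**Conclusion.** The inconsistency is real and unexplained: both adjusted CAFS sets omit a covariate that the SAP adds, for its prognostic strength, to the adjusted models of the outcome CAFS ranks first. Its effect is minor. There is essentially no change in standard error if age acts on survival only, and about 0.5% to 3% lower if age also correlates 0.1 to 0.2 with functional change. That correlation, the event risks, the hazard ratios and the number of shared controls are all assumptions. Protection against chance imbalance is a further modest benefit.

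A reader might infer that the omission widens the CAFS interval, or costs the equivalent of up to 10% more participants. The documents support neither. The 10% figure needs a 9.0% fall in residual variance (1/(1 − 0.090) = 1.099). In simulation that arose only under an assumed death hazard ratio of 1.6 per decade together with an assumed age effect on functional slope of 0.20 points per month per decade.

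A related ambiguity in 6.5.5 deserves at least as much attention. One sentence assigns the primary CAFS analysis to the MPRDR. Another says primary CAFS inference is covariate-adjusted, without saying whether set 4 or set 5 is meant. The MPRDR and M-SAP were not available, so the covariates of the analysis defined in the MPRDR could not be checked.

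**What to change.** Add baseline age, as a continuous covariate, to items 4 and 5 of SAP 6.5.5 for ALSFRS-R, HHD upper and lower extremity percentage, and SVC.

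In the same edit, state which of the two sets the specified covariates refers to for primary CAFS inference, and how that inference relates to the primary CAFS analysis in the MPRDR. The precedence table in SAP section 1 does not settle this, because both statements stand within the R-SAP.

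The change should be fixed before unblinded results are seen, so that a chance age imbalance does not start an argument after the fact. It costs one model term and one degree of freedom, needs no new data, and gives up a little alignment with the covariates of the functional models.

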6.5.6 HHD0 and HHD0²

Analyses of HHD0 are the same as specified in the M-SAP with the addition of parallel analyses of HHD0², with a separate analysis that includes baseline serum NfL level as a covariate, and with the clarification that time to zero strength for both analyses is interval censored between HHD assessments.

Inference from these analyses is supportive of inference from the repeated-measures linear mixed model for HHD upper and lower extremity scores.

6.5.7 Quantitative Voice Measures

Given the high frequency of voice recordings, a repeated-measures analysis with unstructured covariance is overly flexible but the assumption of linear change required by the random-slopes model may be overly rigid. To complement estimates from the random-slopes linear mixed model, quantitative voice characteristics will be analyzed in a linear mixed model in which the temporal profile for both fixed and random terms is modeled using cubic B-splines with knots at 8 and 16 weeks. The model will include fixed terms for B-splines (4 terms), treatment group (2 levels), treatment group \times B-spline interaction, centered time since symptom onset and centered time since symptom onset \times B-spline interaction, centered delta-FRS and centered delta-FRS \times B-spline interaction, centered baseline riluzole use and centered baseline riluzole \times B-spline interaction, and centered baseline edaravone use and centered baseline edaravone \times B-spline interaction. The model will include random regimen-specific intercepts and slopes with unstructured covariance, random participant-specific B-splines (5 terms) with unstructured covariance, and a first-order autoregressive structure for residuals. A simplified covariance structure assuming no regimen-level covariance, heterogeneous compound symmetric covariance among the random B-splines, conditional independence of residuals, or a combination of the three simplifying assumptions will be used if the full model fails to converge. The primary estimand will be the treatment-dependent difference in 24-week change from baseline. The estimate and its 95% Wald confidence bounds will be obtained by a linear contrast of adjusted means. A separate analysis will include centered baseline serum NfL level and the interaction of centered baseline serum NfL level and B-splines as additional covariates.

6.5.8 Placebo Multiple Imputation

Placebo multiple imputation analyses are the same as specified in the M-SAP and will be applied to ALSFRS-R total score, HHD upper and lower extremity percentages, and SVC.

The following SAS code specifies the imputation for an endpoint measured every 8 weeks:

```
proc mi data=work.outcomes seed=xxx n impute=50 out=work.out_mi01
    minimum= . . . . x x x x maximum= . . . . y y y y minmaxiter=1000;
    class r1z edv trtrnd;
    fcs reg(Wk08 = sx2b1 dFRS r1z edv Wk00);
    fcs reg(Wk16 = sx2b1 dFRS r1z edv Wk00 Wk08);
    fcs reg(Wk24 = sx2b1 dFRS r1z edv Wk00 Wk08 Wk16);
    mnar model( Wk08 Wk16 Wk24 / modelobs=(trtrnd="0"));
    var sx2b1 dFRS r1z edv Wk00 Wk08 Wk16 Wk24;
run;
```

where Wk00, Wk08, Wk16, and Wk24 are the values of a given efficacy endpoint at the Baseline, Week 8, Week 16, and Week 24 Visits, respectively, trtrnd has a value of zero (0) for participants randomized to placebo, and x and y take appropriate values to specify the range of a given outcome measure (i.e., 0 and 48 for ALSFRS-R total score; 0 and . for HHD upper and lower extremity percentages and SVC).

Inference from these analyses is supportive of inference from the Bayesian shared-parameter, repeated-measures model for the primary endpoint and assess sensitivity to the missing data

assumption of the repeated-measures linear mixed model for secondary endpoints in the FAS analysis set. A separate analysis will include centered baseline serum NfL level as an additional covariate in both imputation stages.

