Abbreviations: ALD = after last dose, ALS = amyotrophic lateral sclerosis, ALSAQ-40 = ALS Assessment Questionnaire, ALSFRS-R = ALS Functional Rating Scale Revised, BP = blood pressure, C = completed only if the visit is conducted in-clinic, CBC = complete blood count, Cln = Clinic visit, CNS-BFS = Center for Neurologic Study Bulbar Function Scale, CSF = cerebrospinal fluid, C-SSRS = Columbia-Suicide Severity Rating Scale, d = day, DNA = deoxyribonucleic acid, ECG = electrocardiogram, LFTs = liver function tests, MP = Master Protocol, PD = pharmacodynamic, Phn = Phone visit, PK = pharmacokinetic, RGA = the zilucolan regimen, Scrn = Screening Visit.

¹ Master Protocol (MP) screening procedures must be completed between 42 days and 1 day prior to the Baseline Visit. If initial administration of conjugate and serotype B meningococcal vaccines is required, then MP screening procedures must be completed no fewer than 14 days prior to the Baseline Visit.

² RGA regimen-specific screening procedures must be completed no more than 41 days prior to the Baseline Visit. If initial administration of conjugate and serotype B meningococcal vaccines is required, then RGA regimen-specific screening procedures must be completed no fewer than 14 days prior to the Baseline Visit. Otherwise, RGA regimen-specific screening procedures may be completed on the same day as the Baseline Visit.

³ Participants should be instructed to hold the morning dose of study drug on the day of the Week 8, 16, and 24 study visits. Study drug should not be taken until after study visit procedures are complete.

⁴ Participants who are participating into the Open-label Extension (OLE) at the time scheduled for the Follow-up Safety Call will not complete a Follow-up Safety Call. Participants who continue into the OLE and then terminate prior to the time scheduled for the Follow-up Safety Call should be asked to complete a Follow-Up Safety Call.

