3.6 Missing Data

Handling of missing data is the same as described in the M-SAP. Clinic-based assessments that are missing due to COVID-19 restrictions or disruptions are considered missing at random.

4. Study Endpoints

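### Placebo multiple imputation fills missed Week 8 and 16 SVC and HHD values without using an observed Week 24 value, which weakens the Week 24 imputation model (minor)

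*SAP*

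**What the plan says.** The code in SAP Section 6.5.8 has three sequential regressions: "fcs reg(Wk08 = sx2b1 dFRS r1z edv Wk00", then "fcs reg(Wk16 = sx2b1 dFRS r1z edv Wk00 Wk08", then "fcs reg(Wk24 = sx2b1 dFRS r1z edv Wk00 Wk08 Wk16". The revision history for version 3.0 records sequential regression as an intended choice. All three visits are placed under a placebo-fitted MNAR statement: "mnar model( Wk08 Wk16 Wk24 / modelobs=(trtrnd='0". The step opens with "proc mi data=work.outcomes seed=xxx n impute=50 out=work.out_mi01" and has no `BY _Imputation_` statement.

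In the schedule of activities (SAP Section 2.9), SVC and muscle strength carry the code C at Weeks 8 and 16, where "C = completed only if the visit is conducted in-clinic", and an unconditional X at Week 24. Note 5 to that schedule allows Weeks 4, 8 and 16, but not Week 24, to be remote in a pandemic; Section 6.1 of the regimen appendix adds other reasons. ALSFRS-R stays on the list of remote procedures. SVC and HHD are not on it.

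SAP Section 3.6 states: "Clinic-based assessments that are missing due to COVID-19 restrictions or disruptions are considered missing at random".

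Section 6.5.8 gives the analysis two roles: support for the primary model, and a test of the missing-data assumption in the mixed model used for the secondary endpoints.

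**The concern.** Regressing each visit on earlier visits is sound when missingness is monotone. Here a participant with a remote Week 16 and a clinic Week 24 has a gap before an observed value. The code draws that Week 16 value as if Week 24 were unknown, and then uses it as a predictor when fitting the Week 24 model. Drawn values of this kind carry no association with Week 24 beyond what Weeks 0 and 8 explain, so the Week 16 coefficient shrinks. A participant who drops out after a steep fall at Week 16 is then projected too mildly.

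A second point is separate. Placebo-based imputation is meant for data after dropout. The MNAR statement also covers Weeks 8 and 16, so an active participant's COVID-related gap is drawn from the placebo model although Section 3.6 calls it missing at random.

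At stake is how well this sensitivity analysis does its job for HHD and SVC, which are in the testing hierarchy.

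**Working it through.** **Inputs.** From the documents: the regressions and placebo-only fitting (SAP 6.5.8), the gap pattern (SAP 2.9), 120 active and 40 placebo participants (regimen appendix), and shared placebo from regimens B, C and D with no number given (SAP 6.1). The documents give no missing rate, dropout rate, slope or SD, and no operating characteristic for this analysis, so there is no plan figure to reproduce. Everything else below is assumed.

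**Step 1: attenuation.** If a fraction q of the rows used to fit the Week 24 model have a Week 16 value drawn without Week 24, the partial covariance of Weeks 16 and 24 falls by about that fraction. To first order the coefficient becomes (1 − q)β. A large-sample simulation (200,000 participants; slope −2.5 points/month, SD 2; residual SD 5; faster decliners drop out) gives β = 0.85 without gaps.

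| Missed per visit | (1 − q) × 0.85 | Simulated | Simulated, same people miss both visits |
|---|---|---|---|
| 10% | 0.77 | 0.80 | – |
| 20% | 0.68 | 0.73 | 0.65 |
| 40% | 0.51 | 0.56 | 0.47 |

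At 20% missed, filling gaps by arm from all visits and then imputing the tail from placebo restores 0.850. All-visit FCS that is still fitted on placebo gives 0.852. The cause is therefore the omission of later visits, not the placebo source.

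**Step 2: imputed change for placebo dropouts.** Same simulation:

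| Missed per visit | As coded | True | Error |
|---|---|---|---|
| 10% | −20.20 | −20.99 | 0.79 |
| 20% | −19.07 | −20.72 | 1.65 |
| 40% | −16.68 | −19.63 | 2.95 |

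At 20% missed, the error runs from 1.2 to 2.6 points over residual SDs of 3 to 8. The two-step version gives −20.62. If dropout is unrelated to decline there is no material shift (−14.06 against −13.96). If slower decliners leave, the shift reverses (−8.64 against −6.98).

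**Step 3: arm contrast.** Observed Week 24 values are untouched, so the change in the contrast is p_A·s_A − p_P·s_P, where p is the dropout proportion and s the mean shift per dropout. Check at 20% missed with an assumed effect of +0.75 points/month. Relative to the two-step version, s_A = −17.67 − (−19.33) = 1.66 and s_P = −19.07 − (−20.62) = 1.55. Then 0.204 × 1.66 − 0.242 × 1.55 = 0.339 − 0.375 = −0.036. The simulated contrasts differ by 3.643 − 3.680 = −0.037. The shifts are in the same direction in both arms and largely cancel.

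Next, an SVC-like endpoint with no drug effect, 120 active against an assumed 160 placebo, slope −2.5 (SD 2.2), residual SD 3.5. Where two figures appear, the second comes from a repeat with a different dropout mechanism.

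| Remote visits | Dropout, active / placebo | Bias as coded (points) |
|---|---|---|
| 0% | 22% / 12% | −0.016 (two-step −0.019) |
| 15% | 22% / 12% | +0.06; +0.09 |
| 30% | 22% / 12% | +0.21 (Monte Carlo SE 0.025); +0.20 |
| 45% | 22% / 12% | +0.38; +0.24 |
| 30% | 17% / 17% | −0.03 |
| 30% | 15% / 13% | +0.02 |
| 30% | 12% / 22% | −0.26 |

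At 30% remote and 22% / 12%, the coefficient falls from 1.06 to 0.78 (0.80 in the repeat). Dropouts' imputed change is −20.4 against a true −23.4 (−20.2 against −22.9 in the repeat). The two-step version gives a bias of 0.00. The 45% figure depends on the dropout mechanism, so its size is uncertain.

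**Step 4: scale.** The sampling SD of the arm difference in this setting is about 1.5 points, and 0.20 / 1.5 = 0.13. A shift of 0.13 SE moves a two-sided 5% test to Φ(−1.83) + Φ(−2.09) ≈ 5.2%. The largest figure, 0.38 / 1.5 = 0.25 SE, gives under 6%.

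**Step 5: Section 3.6 against the MNAR statement.** The conflict follows from the text alone. Its numerical effect is limited: in a complete-data Week 24 contrast, an active completer's filled Week 8 or 16 value does not enter. It matters only where such a value predicts a missing Week 24 value.

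**The case against.** The strongest reply is that Section 6.5.8 adopts the Master SAP method, which is not available here, and ends with "A separate analysis will include centered baseline serum NfL level as an additional covariate in both imputation stages" although only one imputation step is printed. A first stage for intermittent gaps may therefore exist. That possibility stands and the fix allows for it. It does not remove the point: the printed step reads `work.outcomes`, makes 50 imputations and has no `BY _Imputation_`, so as written it does not start from gap-filled data. SAP Section 1 also puts this SAP above the Master SAP where they differ.

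Second, departing from MAR is the purpose of a sensitivity analysis. This holds for data after dropout. It is a weaker defence for gaps that occurred because a visit was remote.

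Third, the effect on the contrast is small, the rates are assumed, and inference for HHD and SVC rests on the mixed model, which uses all observed visits. All of this stands and sets the priority.

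A reader might infer that the analysis favours active treatment, or in general the arm with more dropout, and so gives false reassurance. The documents do not support that. They give no dropout rates. The direction requires dropout that is both informative and unequal, and in the simulations with a true effect the contrast moved toward zero, by about 0.02 to 0.24 points with 10% to 40% missed. Nor do dropouts always look better than they are: with an effect of +0.75 points/month, active dropouts are imputed at −17.67, milder than the placebo-reference target of about −19.2 but worse than their actual −16.89.

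**Conclusion.** The point holds in a limited form. The printed code is unsuited to the gap pattern that the schedule makes foreseeable for SVC and HHD, and it attenuates the Week 24 imputation model. When faster decliners drop out, their imputed Week 24 values are too mild against the placebo-reference target, by about 1 to 3 points over most of the assumed range. The arm contrast is materially biased only when dropout also differs by arm: about +0.2 SVC points at 30% remote visits with 22% against 12% dropout, about zero with equal dropout, reversed if placebo loses more, and nil without intermittent gaps. That is small beside a standard error of about 1.5 points.

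The use of the placebo model for COVID-related gaps is a separate inconsistency with Section 3.6 and does not cause the attenuation. ALSFRS-R is collected remotely and is largely unaffected. Priority: minor.

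**What to change.** Replace the code in SAP Section 6.5.8 with two steps.

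1. Fill intermittent gaps under MAR, separately by arm, conditioning on all observed visits: `PROC MI` with `MCMC IMPUTE=MONOTONE`, or FCS with all other visits as predictors. ALSFRS-R, which is collected at remote and phone visits from Week 4, could be added as an auxiliary predictor for SVC and HHD.
2. Run the sequential placebo-based regressions with the MNAR statement by `_Imputation_`, only on the monotone tail after each participant's last observed visit.

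If the Master SAP already contains the first stage, say so and make the printed code read its output. One sentence should also confirm that COVID-related gaps follow Section 3.6 here.

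The cost is some extra programming and validation. No new data are needed, and the primary and main secondary analyses do not change.
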